Study Population:	
Approximately 146 individuals will participate in this study. The number is approximate because for focus group discussions, the number of participants can range from 6-10.
 
Aim 1:
 
 
• Focus group discussions (approximately 96 participants): Participants will be patients with hypertension who are currently enrolled in the AMPATH CDM program, and at least 18 years of age from the counties of Bungoma, Trans Nzoia, and Uasin Gishu in Western Kenya. Clinical staff in the AMPATH CDM program and community leaders from the counties will also participate. (12 total FGDs, 6-10 participants each)
 
• Key informant interviews (4 participants): Participants will be County Executive Committee representatives for health from the three Counties included in the study and the Ministry of Health head for non-communicable diseases (NCDs).
 
 
Aim 2:
 
 
• Human Centered Design Team (20 participants): Participants will be individuals representing the following stakeholder groups: research team members, clinicians, pharmacists, peers, patients with hypertension, representatives from the informatics team, and other relevant staff members involved in hypertension care
 
 
Aim 2.1:
 
 
• Use of Survey tools adapted from acceptability and appropriateness measures (39 participants):
 
• Participants will be patients (as described above), peer navigators, and clinical staff (as described above).
 
 
Aim 2.2:
 
 
• Pilot (up to 100 participants): Participants will be patients who are currently enrolled in the AMPATH CDM program, and at least 18 years of age from the counties of Bungoma, Trans Nzoia, and Uasin Gishu in Western Kenya.
 
• Retrospective comparator group: AMRS records of up to 100 patients who will serve as a control group matched by sex, age, location and initial blood pressure level
 

Phase* or Stage:	N/A
Description of Sites/Facilities Enrolling Participants:	AMPATH catchment area in three counties of western Kenya: Bungoma, Trans Nzoia, and Uasin Gishu.

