staff and peers will receive study specific training on the need to at all times maintain participant confidentiality, in addition to receiving training in good clinical practice (GCP) and human subjects' protection (HSP) training. The HIT platform builds on the AMPATH OpenMRS system which encompasses patient data protection measures such as restricted access to authorized users only, which will further maintain patient confidentiality. We will recruit **up to 100** patients from among these three facilities, targeting an equal number per county. In case there is a report of an adverse reaction to medications or new symptom by the participant to the peer during the pilot phase of the study, all peer navigators will be guided by a decision support system built into the HIT that will require the prompt notification of one of the two local pharmacist investigators in the study, as well as the patient's clinician. The peer will contact directly both the pharmacist investigator(s) and the appropriate clinician. Swift action will be taken based on the advisement of the clinician. Inclusion criteria will include age greater than 18 years, and currently enrolled in the AMPATH CDM program. Exclusion criteria will include acute illness requiring immediate medical attention, terminal illness, or inability to provide informed consent.

We will collect data through a survey on process and implementation measures such as completeness of the peer delivery, satisfaction of the patients, patient activation, and fidelity of delivery strategy. We will conduct FGDs with patients and clinicians then conduct KII (Key informant interviews) with the peer delivery agents, focusing on contextual issues impacting implementation, suggestions for modifications, and concepts of feasibility (Table 3). The target group size for the FGDs is 6-10 participants but if there are insufficient numbers, we will accommodate a smaller size. FGD transcripts, data management, and analysis will be performed as described above. We have used this approach previously with success.

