For Aim 2, the clinician will invite AMPATH CDM Program patients with uncontrolled hypertension and who are eligible for the study from the health facility to enroll in the study on the day of their routine clinic visit. On that day, research team members will describe the research study and the study protocol, and ensure the patient meets eligibility criteria. For patients randomized to the PT4A intervention arm, participants will be informed the Health Information Technology (HIT) functionality and the availability of peer delivery agents who can deliver the medications to them. As above, extreme care will be taken to fully explain the benefits and risks of the research study, before consent is obtained. Written informed consent will be obtained from all participants. For Aim 2, activities requiring a consent form are the human-centered design FGD and the human-centered design survey. For Aim 2.1, a consent form will be developed and implemented to obtain written informed consent to participate in the FGD. Finally, for Aim 2.2, consent forms will be developed and implemented to obtain written informed consent in the Aim 2.2 FGD and participation in the pilot study. The consent forms will be written in lay terminology at approximately 6th grade level. For FGDs, written informed consent will be obtained in the same manner as above.

Individuals will be free to refuse to participate in the study at any time during the period of the study. A refusal will not impact the health care available to the individual in any manner. Access to care will not be impacted in any manner by an individual's decision to opt out of this research project.

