			Code and analyze qualitative data	M6	100% of transcripts coded and analyzed	# transcripts coded and analyzed	NVivo database	Challenge: Difficulties in harmonizing qualitative data analysis across multiple regions Mitigation: Documenting context-specific differences that arise from the transcripts; ensure that qualitative analysis team consists of individuals representing all regions and countries
Aim 2 Use a human-centered design approach to refine and adapt the PT4A strategy	Refine the poor delivery and HIT components	1. Human-centered design process	Conduct human-centered design process	M8	100% of brainstorming, conceptualization, and creation of process completed	# of HCD sessions completed	Sign-in sheets from sessions	Challenge: Delays in assembling HCD team with adequate representation of all key stakeholders, and difficulty scheduling sufficient sessions based on stakeholder and project staff availability Mitigation: Incorporate additional time for any additional unforeseen time barriers/institutions requirements that may delay recruitment and implementations, and adjust schedule as necessary
			Conduct FGDs with patients, peers and clinical staff	M9	100% of all interviews conducted	# of interviews conducted	Interviews	Challenge: All challenges from qualitative data collection from Aim 1 above will apply Mitigation: All mitigation from qualitative data collection from Aim 1 above will apply, as appropriate
		3. Conduct a pilot of the intervention and evaluate feasibility.	Code and analyze qualitative data	M9	100% of transcripts coded and analyzed	# transcripts coded and analyzed	NVivo database	Challenge: All challenges from qualitative data collection from Aim 1 above will apply Mitigation: All mitigation from qualitative data collection from Aim 1 above will apply, as appropriate
			Pilot implementation	M11	100% of pilot activities implemented	# of patients who were recruited and received pilot intervention	REDCap database	Challenge: Unforeseen delays in county engagement; lower-than-anticipated enrollment Mitigation: Community-based screening events, community entry, clinician engagement, approval from clinic and regional administrators

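### The planned recruitment count cannot give pilot uptake among eligible patients, and the SBP contrast sets consenting enrollees against matched records that had no invitation or consent step

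*Combined protocol and SAP*

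**What the plan says.** All references are to the combined protocol and SAP.

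- **Invitation.** The Aim 2 paragraph of Informed Consent and Assent states that "the clinician will invite AMPATH CDM Program patients with uncontrolled hypertension and who are eligible for the study from the health facility to enroll" during a routine clinic visit. After that, "research team members will describe the research study and the study protocol, and ensure the patient meets eligibility criteria". No rule says which eligible patients are approached, and no log of eligible, invited or declining patients is described.
- **Recruitment measure.** In Table 4 (Milestones), the Pilot implementation row has the goal "100% of pilot activities implemented" and, as its metric, the number "of patients who were recruited and received pilot intervention". The same row lists "lower-than-anticipated enrollment" as an anticipated challenge.
- **Size.** Sub-Aim 2.2 plans up to 100 "patients from among these three facilities, targeting an equal number per county". Appendix A repeats the ceiling but also gives ten per facility, which is 30 over three facilities.
- **Other pilot measures.** Delivery completeness, satisfaction, activation and fidelity are all measured in enrolled patients. Uptake otherwise appears only as an opinion question in the clinical-team and peer interview guides. Intention to participate is surveyed in the separate Sub-Aim 2.1 convenience sample of 39.
- **Comparator.** The synopsis specifies "AMRS records of up to 100 patients who will serve as a control group", matched on sex, age, location and initial blood pressure. Sub-Aim 2.2 uses the difference in blood pressure change to gauge the size and variability of the PT4A effect.

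**The concern.** A pilot that precedes a cluster randomized trial is the natural place to learn what share of eligible patients will accept door-to-door delivery. The plan expects enrolment might fall short, yet the only quantitative recruitment measure is a numerator that merges joining with receiving. Denominators not written down during recruitment are hard to rebuild afterwards.

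The same gap affects the blood pressure comparison. Enrollees attended clinic, were approached and agreed to take part. Comparator records passed through no invitation or consent step. The protocol's own preliminary data show that engagement varies widely in this population: 62% of hypertensive patients reported a missed or skipped refill, and an audit found that only 24% of those due for a refill came back for it. Engagement plausibly affects adherence and blood pressure, and none of the four matching variables measures it directly.

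**Working it through.** The documents give no uptake, precision or power figure for the pilot, so there is nothing to reproduce. Denominators, SDs and selection differences below are assumptions.

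**1. What the count identifies.** Let E be eligible patients (for simplicity, all invited), C those consenting and D those consenting who received PT4A. The plan reports D. Uptake is C/E and receipt is D/C. Three cases with D = 80:

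| E (assumed) | C (assumed) | D | Uptake C/E | Receipt D/C |
|---|---|---|---|---|
| 100 | 80 | 80 | 80% | 100% |
| 100 | 100 | 80 | 100% | 80% |
| 400 | 100 | 80 | 25% | 80% |

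The milestone value is the same in all three.

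**2. What other planned data recover.** Written consent is obtained from every participant, so C is known. Each delivery is signed for in the HIT tool, so D and continued delivery are known. D/C and the share still on delivery can therefore be computed, although neither is specified. E, and the numbers invited and declining, are recorded nowhere, so C/E cannot be computed.

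**3. Precision if denominators were kept.** The 95% half-width is 1.96 × √(p(1−p)/n), with n the denominator of the proportion concerned.

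- Proportions of consenters, worst case p = 0.5: n = 100 gives 1.96 × √(0.25/100) = 0.098, about 10 points. n = 30 gives 1.96 × √(0.25/30) = 0.179, about 18 points.
- Consented/eligible, with 100 of an assumed 400: 1.96 × √(0.25 × 0.75/400) = 0.042, about 4 points.
- Wilson intervals for uptake at other assumed denominators: 100/125 = 80% (72 to 86%), 100/200 = 50% (43 to 57%), 30/60 = 50% (38 to 62%), 30/120 = 25% (18 to 33%).

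**4. Sensitivity of the SBP contrast.** Treat the groups as unpaired, with an assumed SD of SBP change of 15 to 25 mmHg and two-sided alpha 0.05. Then SE = SD × √(2/n). With no PT4A effect and a selection difference b favouring enrollees, the chance of a nominally significant result in PT4A's favour is about Φ(b/SE − 1.96).

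- n = 100 per group: SE = 15 × √0.02 = 2.12 to 25 × √0.02 = 3.54 mmHg.
  - b = 4: Φ(4/2.12 − 1.96) = 47% down to Φ(4/3.54 − 1.96) = 20%.
  - b = 2: 16% down to 8%.
  - b = 0: Φ(−1.96) = 2.5%.
- n = 30 per group: SE = 3.87 to 6.45 mmHg. b = 4 gives 18% down to 9%.

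For scale, the only effect size in the documents is a reduction of nearly 6 mmHg in an earlier peer-delivery pilot.

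**The case against.** The case on the other side is substantial, and most of it limits the point rather than removing it.

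- **The milestone can never fail.** A reader might infer this from a bare count with a ceiling and no minimum. The stated goal, however, is "100% of pilot activities implemented", which refers to activities, and activities can be left undone.
- **Clinicians hand-pick patients.** The text does not say so. It can equally be read as inviting every eligible patient. Discretion is only left open by silence, and the same paragraph mentions randomized patients although the pilot has no randomization, so it is an uncertain guide to pilot recruitment.
- **The comparator is uncontrolled.** It is not. Four matching variables are named, and the comparison is descriptive rather than a formal test. That lessens the concern. It does not supply a measure of engagement.
- **Receipt and continuation are unknowable.** They are not, as step 2 of the working shows. What is missing is a plan to report them.
- **Table 4 is a grant-tracking table, and Table 3 defines feasibility by perception.** Both are true, and wanting uptake as well is partly a preference. But no other section defines a recruitment measure. Table 4 already pairs a count with a percentage in its SOP row, so the format allows one.

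The missing invitation rule and log, and the unmeasured difference in engagement, remain.

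**Conclusion.** The point holds in a limited form. From the data the plan collects, uptake among eligible patients cannot be estimated or reconstructed: one count is compatible with anything from 25% to 100% in the assumed examples. Receipt and continuation among consenters are a reporting gap only.

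The SBP contrast mixes willingness to join and engagement with care into the PT4A effect, and the stated matching does not remove this. The documents do not give the size of that bias. The figures of 20 to 47% (4 mmHg) and 8 to 16% (2 mmHg) at 100 per group depend on the assumed SDs, an unpaired analysis and an assumed selection difference. Because the comparison is exploratory, this is an improvement worth making before recruitment, not a flaw that invalidates the pilot.

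**What to change.** 1. **Informed Consent and Assent (Aim 2).** State that every consecutive eligible patient on a recruitment day is invited. Keep a tally by facility of eligible, invited, consented, first delivery received and still on delivery at pilot end. Two definitions must be reconciled first. This section refers to uncontrolled hypertension, while the Sub-Aim 2.2 inclusion criteria list only age and CDM enrolment. The pilot lasts up to 1 year in the main text but 3 months in Appendix A.
2. **Table 4, Pilot implementation.** Replace the count with consented/eligible, at least one delivery/consented and still on delivery/consented. Give each a 95% interval on its own denominator.
3. **Sub-Aim 2.2, SBP contrast.** Match or adjust on clinic visits kept before the index visit, where AMRS holds that history for both groups. Add a category for patients enrolled in CDM for less than 12 months. State that this reduces volunteer bias without removing it.

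**Cost.** A short tally on each recruitment day and an attendance extract from AMRS. The proportions may look less favourable than a bare count, and attendance history will be incomplete for recent enrollees. The documents list scheduling and missed-visit follow-up as AMRS functions but do not confirm that the history is complete, so this should be checked first.

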**TABLE 4: PT4A MILESTONES1****Timeline**

	M1	M2	M3	M4	M5	M6	M7	M8	M9	M10	M11	M12
Preparatory Phase												
Finalize protocol manuals												
Finalize standard operating procedures												
Develop data collection tools												
IRB approval												
Hire and train staff												
Aim 1												
Focus Group Discussions												
Key Informant Interviews												
Analysis												
Aim 2												
Human-Centered Design Process												
Sub-Aim 2.1												
Acceptability and Appropriateness Testing												
Sub-Aim 2.2												
Pilot Implementation												
Feasibility Testing												
Analysis												
Research Products												
Community dialogue and input	*	*	*	*	*	*	*	*	*	*	*	*
International Advisory Committee Meetings			x									x
International Conferences									§			§
Publications								‡				‡
R01 Grant Application						Δ						

## APPENDIX A.

### PT4A AIM 2 STUDY PROTOCOL

Project Title: Human Centered Implementation Research for refining and adapting the Peers and Technology for Adherence, Access, Accountability and Analytics (PT4A) Strategy.

**Abstract:** Medication adherence is a much needed avenue of recourse in order to reduce cardiovascular disease (CVD) and death resulting from complications of high BP. To address these hurdles, we hypothesize that the PT4A strategy, which has a component of peer delivery of medication and Health Information Technology, can be an effective implementation strategy to positively influence several micro- and macro-level factors leading to improved adherence to hypertension medications. In this study we will use the human centered design (HCD) approach to refine this proposed strategy. HCD is increasingly applied to implementation research, and it has successfully been used in previous studies. This process starts with the people you are designing for and ends with new solutions that are tailor-made to suit their needs. It builds upon participatory action research, and our protocol includes: patients who are hypertensive, clinical teams providing care to the patients, and community members, who will provide insights on HTN management in a community setting. Initial stages usually revolve around immersion, observing, and contextual framing in which innovators immerse themselves with the problem and community. Subsequent stages may then focus on community brainstorming, modeling and prototyping, and implementation in community spaces. The PT4A Strategy will undergo the following human-centered design processes: the Inspiration phase, Ideation phase, and Implementation phase. An HCD team consisting of individuals representing stakeholder groups: research team, clinicians, pharmacists, peers, patients with hypertension, informatics staff, and other providers involved in hypertension care will go through a participatory and iterative process to help in refining this implementation strategy.

In the Inspiration phase we will learn directly from the people we are designing for. In this case using qualitative research methods as described in Aim 1, we will conduct a thorough baseline contextual assessment of barriers and facilitators for implementing PT4A, and will gain a deeper understanding of the patients, community, and healthcare workers needs and opportunities for solutions. The interview questions employed participatory techniques that elicited emotional elements and promoted group interactions.. The information that will form the guiding themes that will inform the PT4A strategy refinement include: (a) perception of adherence to hypertension medication, (b) perception of HIT, (c) perceptions regarding the role of social support, (d) perception of peer delivery, and (e) factors that may impact the success of the PT4A strategy.

We will explore insights into tangible ideas, divergence and convergence coming closer to the solution that can work best. It is the expectation that team members can have varying ideas when giving solutions but through the process we are able to get a solution that can work and is acceptable with many.

In the Ideation phase we will make sense of the information learned, identify opportunities for design, and prototype possible solutions. During this phase we will look at the actionable items around the core structure of using a peer to deliver medication and the use of the mobile device as a health information support tool.

In the Implementation phase we will bring the solution to life, and eventually, to implementation in the real world. Once the refined PT4A strategy model is developed, we will conduct o assess acceptability and appropriateness. Participants will be recruited through convenience sampling and will provide written informed consent. The initial prototype diagrams will convey key

features of the strategy to the participants and depicted use from the patient, clinician, and peer delivery agent perspectives.

## **PARTICIPANTS**

A team consisting of individuals representing stakeholder groups (in total number 20): research team, clinicians, pharmacists, peers, patients with hypertension, informatics staff, and other providers involved in hypertension care will make up the design team. They will be recruited from across the three counties participating in the study. Participants will be reimbursed for their time, transportation and will be served a snack during design team meetings.

## **METHODOLOGY:**

The design team (DT) will meet for a total of 6 meetings over the course of the process, in order to develop and iteratively adapt the integrated door to door peer delivery of medication and Health Information Technology (HIT) intervention.

**Preliminary Activities:** Baseline information will directly inform our design process. Data collected using qualitative methods that consist of key informant interviews and focus group discussions on the Micro and Macro level contextual factors (individual, family, clinician, health system) that might influence the implementation of the PT4A strategy will be presented before commencing our HCD design process; information on this process can be found in the parent study protocol.

**Baseline Technology:** All of the HIT components will build upon, and be aligned with, the AM-PATH Informatics infrastructure that has been established.

Our PT4A intervention will augment AMRS to support peer-based intervention in four ways:

- 1) Decision support and tailored adherence counseling: provide a patient-level and historical adherence summary that includes pill count, self-report, and clinical data synced with AMRS to generate tailored adherence counseling;
- 2) Teleconsultation: facilitate teleconsultation via text or phone call between the patients and clinicians, by the help of the peer.
- 3) Tracking and accountability: provide timely prompts to peers when refills are near due, and capture participant signature to confirm receipt of medications to improve accountability.
- 4) Analytics: patient-level medication use analytics to predict future stock requirements for pharmacy supply chain. The specific design and implementation of the above will be iteratively improved via the participatory design process.

**Design Process Goals:** The Design Team will be asked to identify and prototype potential solutions to issues raised in the baseline needs and contextual assessment, in addition to the following 4 core elements of the integrated HIT, the door-to-door medication delivery, and peer support intervention:

